FACT-Leu	Functional Assessment of Cancer Therapy-Leukemia		
FAS	Full Analysis Set		
FLAG-IDA	Fludarabine, cytarabine and granulocyte colony-stimulating factor with idarubicin		
FLT3	FMS-like TyrosineKkinase		
GD	Global Development		
GVHD	Graft-versus-host disease		
Н	High		
HSCT Hematopoietic Stem Cell Transplant			
IAP	Interim Analysis Plan		
ICF	Informed Consent Form		
ICH	International Conference on Harmonization		
IDMC	Independent Data Monitoring Committee		
IND	Investigational New Drug		
INR	International Normalization Ratio		
IRT	Interactive Response Technology		
ISN	International Study Number		
ITD	Internal Tandem Duplication		
ITT	Intention to Treatment Set		
IU/L	International units/liter		
IV	Intravenous		
L	Low		
LFS	Leukemia-Free Survival		
MEC	Mitoxantrone, etoposide and intermediate-dose cytarabine		
MedDRA	Medical Dictionary for Regulatory Activities		
mg	Milligrams		
Min	Minute		
mL	Milliliter		
mmHg	millimeters of mercury		
MMRM	Mixed-Effect Model Repeated Measure		
mRAS	Modified Response Analysis Set		
msec	milliseconds		
MUGA	Multigated acquisition scan		
N	Number		
N	Normal		
NCI	National Cancer Institute		
NE	Not evaluable		
NR	No Response		
NYHA	New York Heart Association		
OS	Overall Survival		
PD	Protocol Deviation		
PGx	Pharmacogenetics		

Abbreviations	Description of abbreviations
PK	Pharmacokinetic
PKAS	Pharmacokinetic Analysis Set
PPS	Per Protocol Set
PR	Partial Remission
PRO	Patient reported outcome
PT	Preferred Term
PTT	Partial Thromboplastin Time
QD	quaque die, a Latin phrase meaning "every day"
QTc	QT interval corrected for heart rate
QTcF	QT interval corrected for heart rate using Fridericia's factor
RAS	Response Analysis Set
RBC	Red Blood Cell
RR	Interval between 2 consecutive r waves on an ECG
SAE	Serious Adverse Event
SAF	Safety analysis set
SAP	Statistical Analysis Plan
SAS	Statistical Analysis System
SBP	Systolic Blood Pressure
SOC	System Organ Class
SOP	Standard Operating Procedure
TEAE	Treatment Emergent Adverse Event
TKD	Tyrosine kinase domain
TLF	Tables, Listings and Figures
ULN	Upper limit of normal
VAS	Visual analogue scale
WBC	White Blood Cell
WHO	World Health Organization
WHO-DD	World Health Organization – Drug Dictionary

List of Key Terms

Terms	Definition of terms				
Baseline	Observed values/findings which are regarded as the starting point for comparison.				
Enroll	To register or enter into a clinical trial. NOTE: Once a subject has been enrolled, the clinical trial protocol applies to the subject.				
Intervention	The drug, therapy or process under investigation in a clinical study that is believed to have an effect on outcomes of interest in a study (e.g., health-related quality of life, efficacy, safety, pharmacoeconomics).				
Investigational period	Period of time where major interests of protocol objectives are observed and where the test drug or comparative drug (sometimes without randomization) is usually given to a subject and continues until the last assessment after completing administration of the test drug or comparative drug.				
Post investigational period	Period of time after the last assessment of the protocol. Follow-up observations for sustained adverse events and/or survival are done in this period.				
Screening period	Period of time before entering the investigational period, usually from the time of starting a subject signing consent until just before the randomization.				
Randomization	The process of assigning trial subjects to treatment or control groups using an element of chance to determine assignments in order to reduce bias.				
Screening	A process of active consideration of potential subjects for enrollment in a trial.				
Screen failure	Potential subject who signed consent but did not meet 1 or more criteria required for participation in a trial and did not randomize to the trial.				
Study period	Period of time from the first site initiation date to the last site completing the study.				
Variable	Any quantity that varies; any attribute, phenomenon or event that can have different qualitative or quantitative values.				

1 INTRODUCTION

This Statistical Analysis Plan (SAP) contains a more technical and detailed elaboration of the principal features of the analysis described in the protocol, and includes detailed procedures for executing the statistical analysis of the primary and secondary endpoints and other data.

[figure not shown]
The SAP is finalized and signed prior to any of the following: study unblinding, database hard lock, interim analysis, or accumulation of substantial amount of data in an open-label study to ensure lack of bias. For operational efficiency an earlier time is usually targeted and wherever possible, the SAP should be developed in parallel with protocol finalization. For Phase 2-4 studies the SAP should be developed and approved before First Subject In (FSI). If the expected interval between FSI and soft-lock is less than 12 weeks, then the SAP should be approved by 12 weeks prior to the planned date of soft-lock. If needed, revisions to the approved SAP may be made prior to database hard lock. Revisions will be version controlled.

This statistical analysis is coordinated by the responsible biostatistician of GD-US. Any changes from the analyses planned in the SAP will be justified in the Clinical Study Report (CSR).

SAP version 3.0 dated 27 SEP 2018 has described the final analysis of primary, secondary, and exploratory efficacy endpoints with the data cutoff date of 17 SEP 2018. There will be no efficacy analysis performed for the end-of-study report. The End of Study analysis will be performed on safety data only and COVID-19 related data will be listed.

2 FLOW CHART AND VISIT SCHEDULE

Flow Chart

1°: primary; AML: acute myeloid leukemia; FLT3: FMS-like tyrosine kinase; FLAG-IDA: fludarabine, cytarabine and granulocyte colony-stimulating factor with idarubicin; MEC: mitoxantrone, etoposide and intermediate-dose cytarabine; NR: no response; PD: progressive disease

 Table 1
 Schedule of Assessments for ASP2215 Arm

	Screening			Cyc	ele 1		Сус	cle 2	Subsequent Cycles
Activity	(Day -14 to -1)	Day 1	Day 4 ± 1	Day 8 ± 1	Day 9	Day 15 ± 1	Day 1 ± 2	Day 15 ± 1	Day 1 ± 2
Signed ICF	X								
Medical and Disease History	X								
Randomization		X^p							
Physical Examination ^b	X	Xa	X	X		X	X	X	X
Vital Signs	X	Xa	X	X		X	X	X	X
ECOG Performance	X	Xa				X	X	X	X
Prior and Concomitant Medications	X ^c	X	X	X		X	X	X	X
Pregnancy Test for Woman of Childbearing Potential	X ^d	X					X		X
Chest X-ray (or CT of chest) ^o	X								
12-lead ECG ^e	Xg	X		Xs	Xs	X	X		X
Clinical Laboratory Tests (chemistry, hematology, coagulation, urinalysis) ^f	Xg	Xa	Xa	Xa		Xa	Xa	Xa	Xa
Thyroid Function Test ^t	X								X ^t
Coagulation Profile (PT/INR, D-dimer, fibrinogen)	X								
MUGA or ECHO ^h	X								
Ophthalmologic Assessment ⁱ	X						X		X
FLT3 Mutation Status ^j (bone marrow aspirate or whole blood)	X								
Bone Marrow Aspiration and/or Biopsy	X ^k						X^k		X^k
AE/SAE Assessment	X	X	X	X		X	X	X	X
PK (whole blood samples for plasma PK)		Xl		X^{l}		Xl	X^{l}		X ^l
PGx ^m		X							
Patient Reported Outcome Tools ^{q, r}		Xa		X^q		X^q	X	Xq	X
EQ-5D 5L ^r		Xa					X		X
Resource Utilization		Xa					X		X
IRT Transaction Required ^p	X	X					X		X
ASP2215 Dosing at the Clinic ⁿ		X	X	X		X	X	X	X

AE: adverse event; CR: complete remission; CRc: composite complete remission; CRi: complete remission with incomplete hematologic recovery; CRp: complete remission with incomplete platelet recovery; CT: computed tomography; ECG: electrocardiogram; ECHO: echocardiogram; ECOG: Eastern Cooperative Oncology Group; EDTA: ethylenediaminetetraacetic acid; EQ-5D-5L: EuroQol Group-5 Dimension-5 Level Instrument;

FLT3: FMS-like tyrosine kinase; ICF: Informed Consent Form; INR: international normalization ratio; IRT: interactive response technology; MUGA: multigated acquisition scan; PGx: pharmacogenomics; PK: pharmacokinetic; PT: prothrombin time; SAE: serious adverse event

Footnotes continued on next page

- Obtained predose.
- b. Height measurement performed only at screening. Weight measurement should be performed at screening and day 1 of each cycle.
- c. Includes medications taken within 28 days prior to cycle 1 day 1.
- d. Woman of childbearing potential must have a negative serum or urine pregnancy test (minimum sensitivity 25 IU/L or equivalent units of human chorionic gonadotropin) within 72 hours prior to the start of study treatment.
- e. Screening ECG is required. ECG assessment will be evaluated at predose of cycle 1 day 1, cycle 1 day 8, cycle 1 day 15 and day 1 of each subsequent cycle. Predose assessments should be taken within 1 hour before drug administration. The 12-lead ECGs will be recorded in triplicate (3 separate ECGs 10 minutes resting prior to first ECG and at least 5 minutes apart per time point) and transmitted electronically for central reading. The mean QTcF of the triplicate ECG tracings based on central reading will be used for final treatment decisions and AE reporting. If the mean of the triplicate QTcF is > 500 ms at any time point (by either value on ECG tracing printout or central reading), then triplicate ECGs will be repeated (within 2 hours if based on value on ECG tracing printout and as soon as possible if based on central reading). If the repeat ECG confirms a mean of the triplicate QTcF > 500 ms, dosing of ASP2215 will be interrupted for up to 14 days. While ASP2215 may be interrupted temporarily based on value on ECG tracing printout, the central reading should be used for final treatment decisions. Cardiology consult will be obtained as medically indicated. If QTcF resolves to ≤ 480 ms (grade 1 or less) by central reading within 14 days, the subject may resume dosing at the reduced dose.
- f. Urinalysis only required at screening. Uric acid will be tested on days 1, 4, 8 and 15 in cycle 1. Additional laboratory tests should be performed according to institutional standard of care.
- g. Subjects may be screened and randomized from local labs only. However, samples must also be submitted for central read. Labs and/or ECG can be repeated during screening period.
- h. MUGA scans or ECHO (per standard of care) are to be performed at screening for subjects with history of congestive heart failure New York Heart Association Class 3 or 4 (unless MUGA scans or ECHO performed either within 1 month prior revealed left ventricular ejection fraction ≥ 45%).
- i. Ophthalmologic assessment to be performed by visual acuity measurement and ophthalmoscopy during the screening period, day 1 (± 7 days) of cycle 2, day 1 (± 7 days) of every 2 cycles thereafter, and when clinically indicated. In symptomatic subjects, the ophthalmologic assessment should also include slit lamp biomicroscopy, visual fields performed by Humphrey method and optical coherence tomography.
- j. FLT3 mutation status will be assessed from bone marrow sample taken at the screening visit. If bone marrow sample is unavailable (e.g., dry tap), the whole blood sample taken at the screening visit will be used. Subjects must be screened by the central laboratory. All subjects including those with rapidly proliferative disease must have screening sample sent to the central lab. If central result is negative, central FLT3 testing can be repeated during screening period.
- k. Bone marrow samples are required during screening, cycle 2 day 1 and cycle 3 day 1. For subjects who do not achieve a CRc (CR, CRp or CRi), the bone marrow assessments will be repeated at day 1 of every 2 subsequent cycles. For subjects who achieve a CRc (CR, CRp or CRi), bone marrow sampling will be repeated on 1 month after the date of remission and every 3 subsequent cycles or if there is suspicion of relapse in the whole blood. Bone marrow samples are also required at the pre-HSCT visit/end of treatment visit and as clinically indicated. If bone marrow aspirate is unobtainable (e.g., dry tap), an additional EDTA tube of whole blood should be collected instead. Bone marrow aspirate is required, and bone marrow biopsy is preferred. In case of inadequate aspirate, bone marrow biopsy is required.
- 1. PK samples for ASP2215 will be collected on cycle 1 day 1 predose, cycle 1 day 8 predose and at cycle 1 day 15 and day 1 predose of each subsequent cycle (1 hour before drug administration). See Section 7.6 of the protocol.
- m. Whole blood and buccal swab collected at day 1 for optional pharmacogenomic study.
- n. ASP2215 is taken daily at home except for clinic days when it will be taken at the clinic.

Footnotes continued on next page

- o. Chest X-ray (or CT of chest) does not need to be repeated if performed within 2 weeks prior to start of screening.
- p. For the purposes of drug preparation and dispensing activities, IRT transaction may be done prior to the visit and do not need to fall within the protocol visit window.
- q. Includes Brief Fatigue Inventory, Functional Assessment of Chronic Illness Therapy–Dyspnea-Short Forms, Functional Assessment of Cancer Therapy-Leukemia and dizziness and mouth sores items. The BFI will be administered at cycle 1 day 1 predose, cycle 1 day 8 (± 1 day), day 15(± 1 day), cycle 2 day 1 (± 2 days), day 15(± 1 day) and all subsequent cycles day 1 (± 2 days). Functional Assessment of Chronic Illness Therapy–Dyspnea-Short Forms, Functional Assessment of Cancer Therapy-Leukemia and dizziness and mouth sores items will be administered at cycle 1 day 1 predose, cycle 2 day 1 (± 2 days) and all subsequent cycles day 1 (± 2 days).
- r. If possible, patient reported outcome measures should be performed prior to any other assessments on that visit day.
- s. A cycle 1 day 8 ECG will be taken and the central read results will be provided to the site 24 hours after receipt of the tracing. A confirmatory ECG should be performed on cycle 1 day 9 if the mean QTcF from cycle 1 day 1 to cycle 1 day 8 has increased > 30 ms with no other known etiology, based on the central read ECG. On cycle 1 day 8, it is recommended that the ECG is taken as early as possible in the morning and transmitted immediately. In addition, it is recommended that the cycle 1 day 9 visit is scheduled later in the day in order to allow for receipt and assessment of the cycle 1 day 8 central read ECG. This also allows for a subject to be contacted if the cycle 1 day 9 ECG is no longer required. If the cycle 1 day 9 ECG is still required, the result of the central read ECG will be received on cycle 1 day 10, in which the investigator should assess if the ASP2215 dose modification should occur as per the dose interruption or reduction guideline in Section 5.1.2 of the protocol.
- t. Thyroid function tests will be repeated after every 2 cycles of therapy (C3D1, C5D1, C7D1, etc.).

Table 2 Schedule of Assessments for Chemotherapy Arm

	Screening		Cv	cle 1		Cvo	ele 2	Subsequent Cycles
Activity	(Day -14		Day 4	Day 8	Day 15	Day 1	Day 15	Day 1
	to -1)	Day 1	± 1	± 1	± 1	± 2	± 1	± 2
Signed ICF	X							
Medical and Disease History	X							
Randomization		X^p						
Physical Examination ^b	X	Xa	X	X	X	X	X	X
Vital Signs	X	Xa	X	X	X	X	X	X
ECOG Performance	X	Xa			X	X	X	X
Prior and Concomitant Medications	X ^c	X	X	X	X	X	X	X
Pregnancy Test for Woman of Childbearing Potential	X ^d	X				X		X
Chest X-ray (or CT of chest) ^o	X							
12-lead ECG ^e	Xg	X			X	X		X
Clinical Laboratory Tests (chemistry, hematology, coagulation, urinalysis) ^f	X ^g	Xa	Xa	Xa	Xa	Xa	Xa	Xa
Thyroid Function Tests	X							Xs
Coagulation Profile (PT/INR, D-dimer, fibrinogen)	X							
MUGA or ECHO ^h	X							
Ophthalmologic Assessment	Xi					X^{i}		X^{i}
FLT3 Mutation Status ⁱ (bone marrow aspirate or whole blood)	X							
Bone Marrow Aspiration and/or Biopsy	X^k				X^k	X^k		X^k
AE/SAE Assessment	X	X	X	X	X	X	X	X
PGx ¹		X						
Patient Reported Outcome Tools ^{q, r}		X ^a		X^q	X^q	X	X^q	X
EQ-5D 5L ^r		Xa				X		X
Resource Utilization		Xa				X		X
IRT Transaction Required ^p	X	X				X		X
LoDAC or Azacitidine Dosing					See Footnot	e ^m		
MEC or FLAG-IDA Dosing				See Fo	otnote ⁿ			

AE: adverse event; CR: complete remission; CRc: composite complete remission; CRi: complete remission with incomplete hematologic recovery; CRp: complete remission with incomplete platelet recovery; CT: computed tomography; ECG: electrocardiogram; ECHO: echocardiogram; ECOG: Eastern Cooperative Oncology Group; EDTA: ethylenediaminetetraacetic acid; EQ-5D-5L: EuroQol Group-5 Dimension-5 Level Instrument; FLAG-IDA: fludarabine, cytarabine and granulocyte colony-stimulating factor with idarubicin; FLT3: FMS-like tyrosine kinase; ICF: Informed Consent Form; INR: international normalization ratio; IRT: interactive response technology; LoDAC: low-dose cytarabine; MEC: mitoxantrone, etoposide and intermediate-dose cytarabine; MUGA: multigated acquisition scan; PGx: pharmacogenomics; PT: prothrombin time; SAE: serious adverse event *Footnotes continued on next page*

- Obtained predose.
- b. Height measurement performed only at screening. Weight measurement should be performed at screening and day 1 of each cycle.
- c. Includes medications taken within 28 days prior to cycle 1 day 1.
- d. Woman of childbearing potential must have a negative serum or urine pregnancy test (minimum sensitivity 25 IU/L or equivalent units of human chorionic gonadotropin) within 72 hours prior to the start of study treatment.
- e. Screening ECG is required. ECG assessment will be evaluated at predose of cycle 1 day 1, cycle 1 day 15 and day 1 each subsequent cycle. Predose assessments should be taken within 1 hour before drug administration. The 12-lead ECGs will be recorded in triplicate (3 separate ECGs 10 minutes resting prior to first ECG and at least 5 minutes apart per time point) and transmitted electronically for central reading. See Section 7.5.5 of the protocol.
- f. Urinalysis only required at screening. Uric acid will be tested on days 1, 4, 8 and 15 in cycle 1. Additional laboratory tests should be performed according to institutional standard of care.
- g. Subjects may be screened and randomized from local labs only. However, samples must also be submitted for central read. Labs and/or ECG can be repeated during Screening period.
- h. MUGA scans or ECHO (as per standard of care) are to be performed at screening for subjects with history of congestive heart failure New York Heart Association Class 3 or 4 (unless MUGA scans or ECHO performed either within 1 month prior revealed left ventricular ejection fraction ≥ 45%).
- i. Ophthalmologic assessment to be performed by visual acuity measurement and ophthalmoscopy during the screening period, day 1 (± 7 days) of cycle 2, day 1 (± 7 days) of every 2 cycles thereafter, and when clinically indicated. In symptomatic subjects, the ophthalmologic assessment should also include slit lamp biomicroscopy, visual fields performed by Humphrey method and optical coherence tomography.
- j. FLT3 mutation status will be assessed from bone marrow sample taken at the screening visit. If bone marrow sample is unavailable (e.g., dry tap), the whole blood sample taken at the screening visit will be used. Subjects must be screened by the central lab. All subjects including those with rapidly proliferative disease must have screening sample sent to the central lab. If central result is negative, central FLT3 testing can be repeated during screening period.
- k. For MEC and FLAG-IDA, bone marrow samples are required during screening and cycle 2 day 1. Also, an additional bone marrow sample is required at cycle 1 day 15 or later, per institutional guidelines, to assess the need for a second cycle. For LoDAC or azacitidine, bone marrow samples are required during screening, and at cycle 2 day 1 and at cycle 3 day 1. For subjects who do not achieve a CRc (CR, CRp or CRi), the bone marrow assessments will be repeated at day 1 of every 2 subsequent cycles. For subjects who achieve a CRc (CR, CRp or CRi), bone marrow sampling will be repeated at 1 month after the date of remission and every 3 subsequent cycles, or if there is suspicion of relapse in the whole blood. Bone marrow samples are also required at the end of treatment visit and as clinically indicated. If bone marrow aspirate is unobtainable (e.g., dry tap), an additional EDTA tube of peripheral blood should be collected instead. Bone marrow aspirate is required, and bone marrow biopsy is preferred. In case of inadequate aspirate, bone marrow biopsy is required.
- 1. Whole blood and buccal swab collected at day 1 for optional pharmacogenomic study.
- m. LoDAC or azacitidine dosing may continue past cycle 2.
- n. Additional clinic visits are allowed per institutional guideline for subjects receiving MEC (days 1 through 5) or FLAG-IDA (days 1 through 6). MEC and FLAG-IDA are administered for up to 2 cycles depending on response and safety assessments as described in Section 5.1 of the protocol.
- o. Chest X-ray (or CT of chest) does not need to be repeated if performed within 2 weeks prior to start of screening.
- p. For the purposes of drug preparation and dispensing activities, IRT transaction may be done prior to the visit and do not need to fall within the protocol visit window.

Footnotes continued on next page.

- q. Includes Brief Fatigue Inventory, Functional Assessment of Chronic Illness Therapy–Dyspnea-Short Forms, Functional Assessment of Cancer Therapy-Leukemia and dizziness and mouth sores items. The BFI will be administered at cycle 1 day 1 predose, cycle 1 day 8 (± 1 day), day 15 (± 1 day), cycle 2 day 1 (± 2 days), day 15 (± 1 day) and all subsequent cycles day 1 (± 2 days). Functional Assessment of Chronic Illness Therapy–Dyspnea-Short Forms, Functional Assessment of Cancer Therapy-Leukemia and dizziness and mouth sores items will be administered at cycle 1 day 1 predose, cycle 2 day 1 (± 2 days) and all subsequent cycles day 1 (± 2 days).
- r. If possible, patient reported outcome measures should be performed prior to any other assessments on that visit day.
- s. For subjects receiving LoDAC or azacitidine, thyroid function tests will be repeated after every 2 cycles of therapy (C3D1, C5D1, C7D1, etc.).

 Table 3
 Post-treatment Schedule of Assessments

Activity	Pre-HSCT Visit/ End of Treatment Visit ^a	30-Day Follow-up (+ 7 days Post Pre-HSCT Visit/Post End of Treatment Visit)	Long-term Follow-up (+/- 7 days) ^h
Physical Examination	Xb		
Vital Signs	X ^b		
ECOG Performance	X^{b}		
Concomitant Medications	X ¹		
Pregnancy Test for Woman of Childbearing Potential	X		
12-lead ECG	X		
Ophthalmologic Assessment ^j	X		
Clinical Laboratory Tests (chemistry, hematology, coagulation)	Xb		
Thyroid Function Tests	X		
Bone Marrow Aspiration and/or Biopsy	X ^c		
FLT3 Mutations ^d (bone marrow or whole blood)	X		
Patient Reported Outcome Tools ^{i,k}	X		
EQ-5D-5L ^k	X	X	X
Resource Utilization	X		
AE/SAE Assessment	X	X ^{e,f}	X ^g
IRT Transaction Required	X		
Survival and Subsequent Antileukemic Treatments and Their Outcomes		X ^f	X

AE: adverse event; ECG: electrocardiogram; ECOG: Eastern Cooperative Oncology Group; EDTA: ethylenediaminetetraacetic acid; EQ-5D-5L: EuroQol Group-5 Dimension-5 Level Instrument; FLT3: FMS-like tyrosine kinase; HSCT: hematopoietic stem cell transplant; IRT: interactive response technology; SAE: serious adverse event

- a. End of treatment visit is to be performed within 7 days after treatment discontinuation, and before initiation of any other systemic antileukemic treatment or conditioning regimen for HSCT.
- b. Does not need to be repeated if collected at a regularly scheduled visit within 3 days of the end of treatment visit.
- c. Bone marrow aspiration and/or biopsy for morphology are preferred, but biopsy may be omitted if the aspirate is considered to be adequate. If bone marrow aspirate is unobtainable (e.g., dry tap), an additional EDTA tube of peripheral blood should be collected instead.
- d. FLT3 mutation analysis will be performed on the bone marrow samples collected post study treatment.

Footnotes continued on next page

- e. For subjects who plan to proceed to HSCT and resume ASP2215 treatment after HSCT, AE collection will continue until the start of the HSCT conditioning regimen and AE collection will resume upon the resumption of ASP2215 treatment until 30 days after the last dose of study drug. For subjects who do not plan to resume ASP2215 treatment after HSCT, AE collection will continue until the start of the HSCT conditioning regimen or 30 days after the last dose of study drug, whichever comes first. However, the following AE/SAEs will continue to be collected until 30 days after the last dose of study drug, regardless of the time of the HSCT conditioning regimen:
 - Any study drug related AE that is ongoing will be followed until resolved
 - Any SAE that is deemed to be related to study drug by the investigator
 - Any event of veno-occlusive disease (VOD) of the liver, cardiac failure, Grade 3 or higher QT prolongation, rhabdomyolysis, drug-induced liver injury, or PRES
 - Adverse events leading to death
- f. Telephone contact with the subject is sufficient unless any assessment must be repeated for resolution of treatment-related AEs.
- g. Only SAE data that is related to ASP2215 will be collected.
- h. Telephone contact every 3 months. Ad hoc contact will be required during interim analysis.
- i. Includes Brief Fatigue Inventory, Functional Assessment of Chronic Illness Therapy—Dyspnea-Short Forms, Functional Assessment of Cancer Therapy—Leukemia and dizziness and mouth sores items. The BFI will be administered at pre-HSCT/end of treatment visit. Functional Assessment of Cancer Therapy—Dyspnea-Short Forms, Functional Assessment of Cancer Therapy—Leukemia and dizziness and mouth sores items will be administered at pre-HSCT/end of treatment visit.
- j. Ophthalmologic assessment to be performed by visual acuity measurement and ophthalmoscopy, at the Pre-HSCT/end of treatment (+/- 7 days). In symptomatic subjects, the ophthalmologic assessment should also include slit lamp biomicroscopy, visual fields and optical coherence tomography (OCT).
- k. If possible, patient reported outcome measures should be performed prior to any other assessments on that visit day.
- 1. Concomitant medications should be collected for reported AE/SAEs through 30 days post dose for subjects who have discontinued. For subjects who undergo HSCT, concomitant medications should be collected for reported AE/SAEs through start of conditioning treatment or 30 days post dose, whichever comes first.

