3.1.2 Secondary Objectives

The key secondary objectives are to:

- Determine the overall efficacy in event-free survival (EFS) of ASP2215 compared to salvage chemotherapy.
- Determine the overall efficacy in complete remission (CR) rate of ASP2215 compared to salvage chemotherapy.

The secondary objectives are to evaluate the safety and efficacy of ASP2215 therapy versus salvage chemotherapy in terms of:

- Leukemia-free survival (LFS)
- Duration of remission
- Complete remission with partial hematologic recovery (CRh) rate
- Composite complete remission (CRc=CR+CRp+CRi) rate
- Transfusion conversion rate; Transfusion maintenance rate
- Transplantation rate
- Patient reported fatigue (Brief Fatigue Inventory [BFI])
- Adverse events (AEs), safety labs, vital signs, ophthalmologic exams, electrocardiograms (ECGs) and Eastern Cooperative Oncology Group (ECOG) performance scores
- Evaluation of ASP2215 (and metabolites as appropriate) plasma concentration and population pharmacokinetics (PK)

3.1.3 Exploratory Objectives:

Evaluate the safety and efficacy of ASP2215 therapy versus salvage chemotherapy in terms of:

- Pharmacogenomics (PGx)
- FLT3 gene mutation status
 - o mutation types and frequency
 - o relationship to efficacy and safety
 - mechanisms of acquired resistance
- Exploratory (predictive) biomarkers of ASP2215 activity
- Resource utilization in this study population including hospitalization, blood transfusion, antibiotic intravenous infusions, medication for AEs and opioid usage
- Patient reported dyspnea (Functional Assessment of Chronic Illness Therapy-Dyspnea-Short Forms [FACIT-Dys-SF])
- Patient reported signs, symptoms and impacts of AML (Functional Assessment of Cancer Therapy-Leukemia [FACT-Leu], dizziness and mouth sore items)
- EuroQol Group-5 Dimention-5 Level Instrument (EQ-5D-5L)

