- Clinical laboratory variables (hematology, biochemistry including liver function test and thyroid function test)

- Vital signs (systolic and diastolic blood pressure, pulse rate, and body temperature)
- 12-lead electrocardiogram (ECG)
- Ophthalmologic assessment (visual acuity measurement)
- ECOG performance scores

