7.5.7 Ophthalmologic Assessment

Quantitative ophthalmologic variable (logmar score for visual acuity) will be summarized using mean, standard deviation, minimum, maximum and median by treatment group at each visit for each eye.

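### Section 7.5.7 summarises only raw logMAR by visit and eye: no change from baseline, no count of subjects who worsened, and no summary of the scheduled ophthalmoscopy

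*SAP*

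**What the plan says.** **Collection.** Section 2, Table 1 footnote i (ASP2215 arm) and Table 2 footnote i (chemotherapy arm) give the same rule: "Ophthalmologic assessment to be performed by visual acuity measurement and ophthalmoscopy during the screening period", repeated at cycle 2 day 1, every 2 cycles after that, and when clinically indicated. Table 3 footnote j adds the last exam: "Ophthalmologic assessment to be performed by visual acuity measurement and ophthalmoscopy, at the Pre-HSCT/end of treatment". Symptomatic subjects also have slit lamp, visual fields and optical coherence tomography.

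**Objective.** Section 3.1.2 lists these exams among the secondary safety measures: "safety labs, vital signs, ophthalmologic exams, electrocardiograms (ECGs").

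**Analysis variable.** Section 6.2 narrows this to acuity: "Ophthalmologic assessment (visual acuity measurement").

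**Analysis.** Section 7.5.7 is a single sentence: "Quantitative ophthalmologic variable (logmar score for visual acuity) will be summarized using mean, standard deviation, minimum, maximum and median by treatment group", at each visit and for each eye. Section 7.1 adds the number of subjects to every continuous summary. No section of the SAP plans a table of ophthalmoscopy results or of the additional exams in symptomatic subjects.

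**The concern.** The SAP collects two things at each scheduled eye exam and analyses one of them, in the form least sensitive to harm in a few people. A mean or median of raw acuity describes the typical subject still attending. If a drug affects the eyes of an uncommon subset, perhaps in one eye, the centre of the distribution hardly moves. The planned maximum is worst acuity, since logMAR rises as vision falls. With no baseline beside it, it cannot separate new loss from poor acuity present at entry. Ophthalmoscopy, which could show a fundus change before acuity falls, reaches no planned table.

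What is at stake is the completeness of the safety report. The Introduction and Section 3.2.1 restrict the end-of-study analysis to safety, so safety tables are what the current version of the plan exists to produce.

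**Working it through.** The SAP states no figure on this point to reproduce. The check is a comparison of its own safety sections, followed by an illustration of dilution.

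**1. What each scheduled safety measure gets**

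| Measure (SAP section) | Change from baseline | Subject counts |
|---|---|---|
| Laboratory (7.5.2) | yes | outside reference range; grade 3 or 4 |
| Liver tests (7.5.2.1) | as for laboratory | above multiples of the upper limit, on the highest value |
| Vital signs (7.5.3) | yes | criteria combining a level and a change |
| QTcF (7.5.4) | not stated | categories by visit; maximum above 480 msec |
| logMAR (7.5.7) | no | no count of worsening |
| Ophthalmoscopy | no summary | no summary |

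Section 7.1 already defines baseline as the last measurement before the first dose, so a change in logMAR needs no new definition.

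**2. Dilution in the mean (assumed inputs)**

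Arm sizes of 246 and 123 are the planned numbers in SAP Section 4. The share affected, the loss and the SD are assumptions, because the SAP gives none. Full attendance and no loss in the control arm are also assumed.

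- Affected: 0.05 × 246 = 12.3, about 12 subjects.
- Each loses 0.3 logMAR in one eye, split evenly between right and left. Mean shift per eye = 0.05 × 0.3 × 0.5 = 0.0075.
- Standard error of the arm difference with SD 0.2 = 0.2 × √(1/246 + 1/123) = 0.022.
- Ratio = 0.0075 / 0.022 = 0.34.

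**3. Range**

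Now put all losses in the same eye, which favours the mean. Take a loss of 0.2 to 0.3 logMAR and an SD of 0.15 to 0.30. The shift is share × loss. The standard error of the ASP2215 mean is SD/√246, or 0.0096 to 0.0191.

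| Share affected | Mean shift | Shift / SE |
|---|---|---|
| 2% | 0.004 to 0.006 | 0.2 to 0.6 |
| 5% | 0.010 to 0.015 | 0.5 to 1.6 |
| 10% | 0.020 to 0.030 | 1.0 to 3.1 |

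Power to see the shift as a difference between arms (two-sided 0.05) is about 5% to 15% at a 5% share and 9% to 44% at a 10% share. Dilution is strong for uncommon toxicity and weakens as the share rises or the SD falls.

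**4. Number of exams per arm**

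MEC and FLAG-IDA stop after at most 2 cycles (Section 2, Table 2 footnote n). Such a subject has at most two scheduled post-baseline exams: cycle 2 day 1 and end of treatment. An ASP2215 subject who starts cycle 6, for example, has cycles 2, 4 and 6 plus end of treatment, which is four. A worst-value count therefore has more chances to be positive in the arm treated longer. Cycle 2 day 1 is an exam scheduled in both arms.

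**The case against.** The strongest reply is that eye harm has other routes into the report. Section 7.5.1 counts subjects with treatment-emergent adverse events by SOC and PT. AE assessment is scheduled at the same visits as the eye exams, Section 5 puts data from all randomized subjects in listings, and symptomatic subjects have a fuller work-up. This stands. A reader might infer that eye toxicity cannot show at all; the documents do not support that. The gap is confined to acuity loss and fundus findings that are not reported as adverse events.

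A reader might also infer that the SAP tabulates only a mean, without subject numbers. It does not: SD, minimum, maximum and median are planned for each eye, with n. What is missing is the number who worsened.

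A third tempting reading is that a count would establish a significant difference between arms where the mean would not. The SAP plans no test on eye data, and such a contrast would hinge on the assumed number of control cases. The case for the count is that it displays affected subjects.

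It can be said that table layout is left to the TLF specifications and that AE reporting rules belong to the protocol, neither of which is shown. This limits what can be said about investigators' reporting. It does not supply the analysis: Section 6.2 itself confines the variable to acuity, and 7.5.7 follows it. The absence of an eye category in Appendix 3 is not an error, since the SAP gives no reason for one.

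**Conclusion.** The point holds as a moderate gap in safety reporting. The SAP names ophthalmologic exams in its objective and schedules ophthalmoscopy in both arms, but plans no summary of it. It reports acuity in a form that shows neither individual change nor how many subjects worsened, a lower standard than it sets for laboratory tests, vital signs and QTcF. This rests on the text alone.

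The size of the masking rests on assumptions. With about 2% to 5% of subjects affected, the visit mean moves by at most 1.6 of its own standard errors in the cases examined. At 10% with a small SD it can reach 3.1, so masking is not certain. Efficacy endpoints, alpha and decision rules are untouched.

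**What to change.** In Section 7.5.7, with a matching change to Section 6.2, add by arm:

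- (a) change from baseline in logMAR, per eye and visit;
- (b) number and percent of subjects with a prespecified worsening from baseline in either eye, with the number examined as denominator;
- (c) a shift table of ophthalmoscopy from baseline to post-baseline (normal/abnormal, new or worsened).

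Make cycle 2 day 1 the main between-arm comparison for (b) and (c). Show the worst post-baseline value as supportive, beside the number of exams per arm, because of the unequal exam counts shown above.

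The cost is small. The assessments are already scheduled, so the work is SAP wording and a few tables. The downside is that the acuity threshold must be chosen, justified and recorded before the tables are run. The primary report already covers data to 17 SEP 2018, so results against a threshold set now should be read as descriptive.
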